15.4. Study specific or unique noncompliance concerns

Any noncompliance issue impacting the rights, welfare, and safety of human subjects are classified as a Major noncompliance and will be escalated following Beckman Coulter's standard operating procedure(s) and or Corrective Action Preventive Action (CAPA) process.

15.5. Changes to Protocol

In the event the study protocol is amended, Beckman Coulter will provide the Principal Investigator with the protocol amendment(s) and a revised protocol. It is the responsibility of the

 BECKMAN COULTER	Access BNP Clinical Performance Evaluation: Testing and Clinical Concordance Study	Document BNP-02-23 Protocol Version: 2.7
---	---	---

Principal Investigator to determine if the protocol amendment(s) should be submitted for IRB approval.

Protocol amendments that affect the subject rights, safety, or welfare must be submitted to and approved by the IRB. The sponsor must be notified of the approval, in writing, prior to implementation.

Protocol amendments that are unrelated to subject rights, safety, or welfare may be submitted to the IRB at the discretion of the Principal Investigator. The Principal Investigator or designee must notify the sponsor, in writing, when he/she has determined that IRB approval is not required, prior to implementation.

15.6. Reconciliation of Study Material, Supplies and Samples

Sponsor is to supply enough quantities of study materials, supplies, and samples to enable the site to complete the study. The site is required to maintain the inventory of these materials provided and document the reconciliation of these materials.

At the completion of this clinical study, all unused materials, supplies, and samples must be returned to the sponsor or disposed of according to instructions from the sponsor. If materials are disposed at the study site, the Investigator must provide the sponsor with a signed record of disposition.

16. Statistical Considerations

The number of K2 EDTA individual subject samples used in this testing study will be approximately 1100.

All valid testing results of samples collected under protocol BNP-05-24 Access BNP Clinical Subject Sample Collection Enrollment Study Protocol from subjects presenting with a clinical suspicion of new onset heart failure or worsening symptoms suggestive of decompensated or exacerbated heart failure will be included in analysis.

Primary endpoints of the study will be diagnostic accuracy between final clinical site diagnosis (HF and Non-HF), IUO BNP assay testing results and severity assessment utilizing the NYHA class.

Method concordance will be established using the valid testing data from the investigational device Access BNP Assay (**item number D06227**) for Dxl 9000 Access Immunoassay Analyzer (P/N C11137) against the currently marketed Access BNP Assay (**item number 98200, original formulation**) for Access 2 Immunoassay System (P/N 81600N). Positive percent agreement (PPA) and Negative percent agreement (NPA) will be calculated using the data.

The objective is to validate established diagnostic cutoff (rule-out) and assess HF severity on the IUO Access BNP Assay (**item number D06227**) using the Dxl 9000 Access Immunoassay Analyzer (P/N C11137). Corresponding sensitivity and specificity at this cutoff will be established for the intended use population. Diagnostic parameters (i.e., sensitivity, specificity, NPV, and PPV) will be

 BECKMAN COULTER	Access BNP Clinical Performance Evaluation: Testing and Clinical Concordance Study	Document BNP-02-23 Protocol Version: 2.7
---	---	---

defined by subjects' HF status as indicated by the IUO assay(s) relative to subjects' clinical HF diagnosis. Additionally, correlation between Access BNP assay results and severity (NYHA class) will be evaluated using the Jonckheere-Terpstra test. Point estimates, event counts, and a 2-sided 95% score confidence interval will be reported for all relevant endpoints.

In addition to the endpoint results, descriptive statistics such as mean median, standard deviations are to be reported. The results are used to support regulatory submissions for the Access BNP assay in all geographic regions, including but not limited to the European Union and United States (US).

The following requirements are strictly followed to prevent and minimize potential biases:

- Any Dxl 9000 results deemed valid per the instruments' instruction for use cannot be excluded for any reasons other than documented human errors.
- Access 2 valid result can only be excluded from analysis in the case a retest is needed on Dxl 9000 and outside of the 2-hour window of sample removal from the -70C (or colder) freezer. In this case a new sample is thawed and tested on both Dxl 9000 and Access 2. The first Access 2 valid result would be excluded from analysis.
- Discrepancy resolution information may be obtained on individual cases for learning purpose only. Such information is not to be reported in any forms of estimation or statistics.

17. Study Materials

The study materials and supplies that will be provided by Beckman Coulter are:

- Testing Specimen/Samples
- IUO Reagent kits for Beckman Coulter Dxl 9000 Access Immunoassay Analyzer*
- IVD Reagent kits for Beckman Coulter Access 2 Immunoassay System
- IVD Calibrators
- IVD Quality Controls
- Clinical Study Binder – eTMF Florence
- USB Flash Drives (if applicable)
- Dxl 9000 consumables (as needed)

* Inventory of Investigational Use Only (IUO) material must be maintained, and reconciliation procedures provided by Sponsor after study completion must be followed.

Basic lab equipment and supplies are not provided by sponsor such as centrifuges, pipettors, lab coats and gloves. Such supplies are part of site lab operation at the oversight of the Primary Investigator.

 BECKMAN COULTER	Access BNP Clinical Performance Evaluation: Testing and Clinical Concordance Study	Document BNP-02-23 Protocol Version: 2.7
---	---	---

18. Supplemental Materials Provided

APPENDIX A: Investigator Protocol Signature Page PROTOCOL SIGNATURE PAGE

Protocol: Access BNP on Dxl 9000 Clinical Performance Evaluation:
Specimen Testing and Clinical Concordance Study

Protocol Number: BNP-02-23

Version: 2.7

Site Name: _____

The signature below attests that I have read and understand the contents of this protocol (or revisions to the protocol) and will adhere to the study protocol requirements as presented including all statements regarding confidentiality, and according to local legal and regulatory requirements and applicable U.S. Federal Regulations and ICH guidelines.

Investigator Printed Name: _____

Investigator Signature: _____

Date (dd/mmm/yyyy): _____

**Access BNP Clinical Performance Evaluation:
Testing and Clinical Concordance Study**

Document BNP-02-23

Protocol Version: 2.7

Content Change Abstract

Revision Level	Date	Author Name	Change Description
1.7	1/19/2024	[name]	Initial Release
1.13	6/18/2024	[name]	
 Cover Page: Updated DHF deliverable number and sponsor address. Removed "Assay" from the document title. Updated the Long Title on header and title page for purposes of better accuracy. Short title and protocol ID remains unchanged. List of Abbreviations: Added AMR, CKD, and eTMF. Throughout document: 
 Corrected name of Access 2 from Analyzer to Immunoassay System Clarified EDTA sample type if K2 EDTA Changed source of samples from HF-01-19 to BNP-05-24. Updated the number of samples to approximately 1100 per BNP-05-24. Updated from Original Formulation to Formulation as per K033383. Refer to the Access BNP assay as the "currently marketed Access BNP" for clarification. Section 2 Study Synopsis 
 Updated the purpose statement for improved clarity of the research purpose to validate a comparison of results. Study Duration has been extended to 12 months to accommodate a fresh blood draw sample requirement. Target Population updated. Samples to be tested will now be from a prospective blood draw study (BNP-05-24 protocol ID). Samples will continue to be frozen in the -70C or colder temperature requirement. Testing will be in parallel within the sample stability claim of 60 days (-20C). Updated inclusion and exclusion criteria. No inclusion criteria as samples come from BNP-05-24. Exclusion criteria is testing samples with HIL observation of 4+ hemolysis or icterus.

**Access BNP Clinical Performance Evaluation:
Testing and Clinical Concordance Study**

Document BNP-02-23

Protocol Version: 2.7

Revision Level	Date	Author Name	Change Description
			
-Study Design updated to a minimum of three (3) calibrator lot and three (3) IUO reagent pack lots will be used in this study.
 
Each site will be provided a minimum of one (1) unique calibrator lot and minimum of three (3) individual IUO reagent pack lots from Sponsor. The IUO reagent lots will be delivered at designated time points determined by Sponsor.
 
 • Update to section 6.3 to reflect subjects are consented under the BNP-05-24 protocol for samples used in this testing study. • Update to section 7.2 Study End Points: "Results are compared against acceptance criteria." • Update to section 8 Study Design - see above and section 2 Synopsis. • Update to section 9.1 For familiarization testing, samples are run on a minimum of 1 calibrator lot and a minimum of 1 reagent lot at the site. • Update to section 9.5 Quality Control Analysis to state results of QC will be evaluated against ranges provided by sponsor, removed number of standard deviations. • Update to section 9.6 QC Acceptance Criteria. Requirement for both replicates of any QC level to fall within ranges provided by sponsor, or the mean of 2 replicates must include one replicate in range. • Update to section 9.8 Sample Handling and Storage Replaced section with new text to follow IFU for sample thaw at room temp for 30 minutes minimum and test within 60 days of collection and 2 hours of sample removal from freezer on both instruments on the same aliquot. Instructions for use of data logger. • Update to section 10.0 Study Flow Chart Replaced flow diagram to reflect updated process steps. • Update to section 11.1 Sample Requirements. To align with enrollment protocol BNP-05-24. No spiking, diluting, depleting, pooling or contrived samples. • Update to 11.3 Investigational Method, Method Comparison Study Procedure Replaced text in this section to include samples to testing sites at approximately monthly intervals, test on both assays on same aliquot

**Access BNP Clinical Performance Evaluation:
Testing and Clinical Concordance Study**

Document BNP-02-23

Protocol Version: 2.7

Revision Level	Date	Author Name	Change Description
			
within 60 days of blood collection and 2 hours removal from -70C freezer. If re-test, must be within 2 hours of removal from freezer. If outside of 2 hours a new aliquot must be tested on both assays / instruments.
 
 Update to section 16 Statistical Considerations. Updated protocol from HF-01-19 to BNP-05-24. Method concordance is to validate against the currently marketed assay. Update to section 17 Study Materials listing study materials and supplies that will be provided by BEC. Update to section 18 Supplemental Materials that will no longer be provided by BEC. Update to section 19, added sixth literature reference. Appendix A: Updated protocol name
Version 2.3	8/21/2024	[name]	
 Overall study changed from Method Comparison to a Clinical Performance Evaluation Testing study. Updated the Full and Short Title on header and title page to reflect the change in study design. Section 2 Study Synopsis 
 Updated the purpose statement to reflect the research purpose to perform specimen testing to support clinical validation and the IUO Access BNP Assay's regulatory approval on the Dxl 9000 Access Immunoassay Analyzer. Updated study objective to is to validate the established diagnostic cutoff (rule-out) and assess HF severity on the IUO Access BNP Assay using the Dxl 9000 Access Immunoassay Analyzer. Updated Study design to reflect min 1 calibrator lot used on this study. Site requirements updated to target of 3 sites will be used for testing. Update to Statistical Methods to reflect study end point is diagnostic accuracy between final clinical site diagnosis (HF or Non-HF) and IUO BNP assay testing results. Update to section 3.2 Study purpose, see above from study synopsis.

**Access BNP Clinical Performance Evaluation:
Testing and Clinical Concordance Study**

Document BNP-02-23

Protocol Version: 2.7

Revision Level	Date	Author Name	Change Description
			
 Section 3.5 Comparator Device Description removed as it is no longer needed. Update to section 3.7 Investigational Sites target of 3 sites will be used for testing Update to section 7.1 Study Objectives to validate established diagnostic cutoffs (rule-out cut-off) and ability to assess HF severity. Update to section 7.2 Study Endpoints Removed Method Comparison and Method Agreement as they are no longer applicable. Changed endpoint to diagnostic accuracy between final clinical site diagnosis (HF or Non-HF) and IUO BNP assay testing results. Update to section 8.0 Study Design to remove reference to method comparison study and related CLSI guideline, reflect the target of 3 external sites instead of 1, and removed reference to testing on the Access 2 instrument. Updated to minimum 1 calibration lot to be used on this study. Removed section 9.4 Comparator Method for calibration and maintenance as it is no longer applicable. Updates to section 9.7 Sample Handling and Storage to remove references to testing on both instruments on the same aliquot and any reference to the predicate Access 2 instrument. Updated section 10 Study Flow Chart to remove reference to testing on Access 2. Removed section 11.2 Comparator Method for calibration and maintenance as it is no longer applicable. New section 11.2 Investigational Method updated to remove testing on the predicate assay. Now will be testing on Dxl 9000 only, 1 run 1 rep... Updated section 12 Assessment of Safety and Product Quality with minor text updates. Updated section 16 Statistical Considerations to reflect new approach and analysis for this clinical performance testing study. Primary endpoints of the study will be diagnostic accuracy between final clinical site diagnosis (HF and Non-HF) and IUO BNP assay testing results.

**Access BNP Clinical Performance Evaluation:
Testing and Clinical Concordance Study**

Document BNP-02-23

Protocol Version: 2.7

Revision Level	Date	Author Name	Change Description
			
 Updated section 17 Study Materials to remove reagent kits for Access 2 as it is no longer needed. Updated Appendix A protocol signature page to reflect the new protocol title.
2.7	9/12/2024, 5:09:43	[name]	
 Overall change to add Clinical Concordance analysis of Dxl 9000 results vs. Access 2. Updated the Full and Short Title on header and title page to reflect the change in study design. Throughout document added part number for Dxl 9000 (C11137) and Access 2 (81600N) Section 2 Study Synopsis 
 Updated Study Purpose to reflect addition of clinical concordance analysis vs BNP assay testing on Access 2. Updated Study Design to add Method Concordance Updated Statistical Method to include Method concordance. Updated section 3.2 Study Purpose to add clinical concordance. Added section 3.5 Comparator Device Description for the Access BNP assay and Access 2 Immunoassay system Updated section 3.8 Investigational site to include the ability to test on the Beckman Coulter Access 2 Immunoassay System. Updated 5.3 Types of Data to include data collected from the Beckman Coulter Access 2 Immunoassay System. Updated section 7.1 Study Objectives to include Method Concordance. Updated section 7.2 Study Endpoints to include Method Concordance. Updated section 8 Study Design to include testing on Access 2 Immunoassay System. Added section 9.4 Comparator Method to note calibration and maintenance of Access 2 instrument should be performed per manufacturer's instructions. Updated section 9.5 Quality Control Analysis to mention how commercial QC on Access 2 is to be run.

**Access BNP Clinical Performance Evaluation:
Testing and Clinical Concordance Study**

Document BNP-02-23

Protocol Version: 2.7

Revision Level	Date	Author Name	Change Description
			
 Updated section 9.8 Sample Handling and Storage to require that testing be completed on both Dxl 9000 and Access 2 on the same aliquot. Updated section 10 Study Flow to include testing on Access 2. A valid result on Access 2 is not required. Added section 11.2 Comparator Method to note calibration and maintenance of Access 2 instrument should be performed per manufacturer's instructions Updated 11.3 Investigational Method to mention repeat testing on Access 2 is not required if valid result on Dxl 9000. Updated section 16 Statistical Considerations: - Any Dxl 9000 results deemed valid per the instruments' instruction for use cannot be excluded for any reasons other than documented human errors. Access 2 valid result can only be excluded from analysis in the case a retest is needed on Dxl 9000 and outside of the 2-hour window of sample removal from the -70C (or colder) freezer. In this case a new sample is thawed and tested on both Dxl 9000 and Access 2. The first Access 2 valid result would be excluded from analysis. Updated section 17 Study Materials to include Access 2 materials. Updated Appendix A PI Protocol signature page with the correct protocol title. Updated Sr Manager approver name

 BECKMAN COULTER	Access BNP Clinical Performance Evaluation: Testing and Clinical Concordance Study	Document BNP-02-23 Protocol Version: 2.7
---	---	---

Approvals

The Project Specific TOC defines the approvers for this document (minimum approvers) and is based on GLB-QS-PCD-0046.

Role	Name	Title
Development (R&D)	[name]	Staff Development Scientist
Development (R&D)	[name]	Director, Development Science
Quality	[name]	Staff Quality Assurance Scientist
Regulatory	[name]	Principal Regulatory Affairs
Regulatory	[name]	Staff Quality and Regulatory Affairs
Selling and Marketing	[name]	Product Manager, CCIA Reagents
Clinical Biostatistics	[name]	Staff Biostatistician
Medical & Scientific Affairs	[name]	Medical Director
Clinical Affairs Author	[name]	Clinical Study Manager
Clinical Affairs Manager	[name]	Senior Manager, Clinical Affairs

My signature confirms my review and approval of this document for its intended use.

APPROVALS:

APPROVED ON: (mm-dd-yyyy)

[name]	09/11/2024 19:22:15 (UTC)
[name]	09/11/2024 19:27:15 (UTC)
[name]	09/11/2024 19:47:25 (UTC)
[name]	09/11/2024 20:33:32 (UTC)
[name]	09/11/2024 20:56:48 (UTC)

## Introduction

The IUO Access BNP assay (P/N D06227) is a paramagnetic particle, chemiluminescent immunoassay for the quantitative measurement of B-type Natriuretic Peptide (BNP) in human plasma using the Dxl Access Immunoassay Analyzers. Diagnostic Accuracy of the IUO Access BNP assay will be evaluated primarily in a multi-center, prospective, study for sensitivity, specificity, Negative Predictive Value (NPV), Positive Predictive Value (PPV), and likelihood ratios (LR). Subjects will be evaluated around a rule-out cutoff.

This statistical analysis plan (SAP) is to provide details in conducting the study and analyses in order to achieve the study objectives and to ensure the quality of study in maintaining internal and external validity of the study.

The study will strictly follow the Access BNP Clinical Subject Sample Collection Enrollment Study Protocol (BNP-05-24) (EDMS title "Access BNP Clinical Enrollment Study") and in compliance with the Good Clinical Practice (GCP) guideline. Additional relevant study background information can be found in the Access BNP on Dxl 9000 Clinical Performance Evaluation: Specimen Testing Clinical Study (BNP-02-23) (EDMS title "Access BNP Clinical Performance Evaluation: Testing and Clinical Concordance Study").

## Purpose and Scope

This statistical analysis plan (SAP) covers study design, statistical analysis method, as well as data quality control for the diagnostic accuracy, where applicable, studies on Access BNP assay running on the Dxl 9000 Access Immunoassay Analyzer. The SAP applies to all clinical studies required for regulatory body or peer reviewed journal submissions, directly conducted and managed by Clinical Affairs.

The results will be used to support regulatory submissions for the Access BNP assay in all geographic regions, including but not limited to the United States and European Union.

### Proposed Intended Use

The intended use is documented in the "BNP 9000 User Needs" document.

 BECKMAN COULTER	Access BNP Clinical Performance Evaluation Statistical Analysis Plan	Document #: NA
------------------------------------------------------------------------------------------------------	---------------------------------------------------------------------------------	--------------------------

## Study Objectives

Diagnostic accuracy of the Access BNP assay will be evaluated in a single prospective, multicenter, clinical study.

The objectives to evaluate the performance of the IUO Access BNP assay:

- To evaluate the clinical utility of the Access BNP assay by validating an established diagnostic rule-out cutoff and ability to assess Heart Failure (HF) severity.

## Endpoints

The following measurements will be reported and evaluated for acceptable performance.

### Primary Endpoints

Primary endpoints of the study will be diagnostic accuracy measured in proportions of sensitivity and specificity between Access BNP assay and final clinical HF status (determined by site diagnosis) and severity assessment measured by correlation between assay results and the New York Heart Association (NYHA) classification.

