3.1. Background

Heart Failure (HF) is a complex medical condition that often exists with other comorbidities. Further, symptoms of HF are nonspecific making HF diagnosis difficult. B-type natriuretic peptide biomarkers (BNP and NT-proBNP) are standard-of-care biomarkers measured at patient presentation in the emergency department (ED) for patients presenting with signs and symptoms suggestive of heart failure. The release of natriuretic peptides (NP) appears to be in direct proportion to ventricular volume expansion and pressure overload. The plasma concentrations of both hormones are increased in patients with asymptomatic and symptomatic left ventricular dysfunction, permitting their use in supporting a clinical diagnosis of HF (but not used alone for this purpose). NPs are well established for use in diagnosis of patients with HF and are included in standard of care guidelines for both the American College of Cardiology Foundation/American Heart Association (ACCF/AHA) and European Society of Cardiology (ESC).^{1,2,3,4}

In the Breathing Not Properly Study, B-type natriuretic peptide test accurately diagnosed HF in patients presenting to the ED with dyspnea, with a sensitivity of 90% and specificity of 76% at a cutoff of 100 pg/mL.⁵ The current commercialized Access BNP assay (primary predicate) for the Beckman Coulter Access Family of Immunoassay Systems has similarly established that BNP results less than or equal to 100 pg/mL are representative of normal values in patients without heart failure.

The Access BNP assay is being redesigned for transference to the Dxl 9000 Access Immunoassay Analyzer (P/N C11137).

Specimen collected under BNP-05-24 "Access BNP Clinical Subject Sample Collection Enrollment Study Protocol" are to be tested on the investigational-use-only (IUO) Access BNP on Beckman Coulter Dxl 9000 Access Immunoassay Analyzer (P/N C11137).

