3.6. Intended Use

Reagent (Item Number D06227)	The Access BNP test is intended for use with the Beckman Coulter Dxl Access Family of Immunoassay Systems for the In Vitro quantitative measurement of B-type natriuretic peptide (BNP) in plasma specimens using EDTA as the anticoagulant. The test is intended to be used for the following indications: 
• as an aid in the diagnosis of congestive heart failure (also referred to as heart failure)• as an aid in the assessment of severity of congestive heart failure• for the risk stratification of patients with acute coronary syndromes• for the risk stratification of patients with heart failure
Reagent (Item number 98200, original formulation)	The Access BNP test is intended for use with the Beckman Coulter Access Family of Immunoassay Systems for the In Vitro quantitative measurement of B-type natriuretic peptide (BNP) in plasma specimens using EDTA as the anticoagulant. The test is intended to be used for the following indications: 
• as an aid in the diagnosis of congestive heart failure (also referred to as heart failure)• as an aid in the assessment of severity of congestive heart failure• for the risk stratification of patients with acute coronary syndromes• for the risk stratification of patients with heart failure

 BECKMAN COULTER	Access BNP Clinical Performance Evaluation: Testing and Clinical Concordance Study	Document BNP-02-23 Protocol Version: 2.7
---	---	---

Calibrators (Item Number 98202)	The Access BNP Calibrators are intended to calibrate the Access BNP test for the quantitative determination of BNP levels in human EDTA plasma using the Beckman Coulter Access Family of Immunoassay Systems.
QC (Item Number 98201)	The Access BNP QC Controls are intended for monitoring the performance of the Access BNP test using the Beckman Coulter Access Family of Immunoassay Systems.

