6.3. Participant Confidentiality

Participant confidentiality is strictly held in trust by the investigators, study staff, and the sponsor(s) and their agents. This confidentiality is extended to cover testing of biological samples and genetic tests in addition to any study information relating to participants.

The study protocol, documentation, data, and all other information generated will be held in strict confidence. No information concerning the study, or the data will be released to any unauthorized third party without prior written approval of the sponsor. Site personnel do not have access to medical standard of care test results or other subject identifying data beyond a sample identification (ID) number for the purposes of conducting this protocol required testing procedures. Only subjects that consented to this use of the collected samples have been included for testing.

The samples used in this testing protocol are collected under protocol BNP-05-24 Access BNP Assay Clinical Subject Sample Collection Enrollment Study Protocol. Samples that will be

 BECKMAN COULTER	Access BNP Clinical Performance Evaluation: Testing and Clinical Concordance Study	Document BNP-02-23 Protocol Version: 2.7
---	---	---

included in analysis after testing are from subjects that were appropriately consented and have not been withdrawn or discontinued, met study inclusion/exclusion criteria, and provided sufficient specimen sample volume required for testing.

Samples collected under protocol BNP-05-24 are anonymized to this protocol's testing sites and in compliance with regulations on data privacy and patient confidentiality.

7. Objectives

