### Additional Endpoints

Additional endpoints include but are not limited to:

- Assay performance in different subgroups (eg: age, sex, comorbidities)
- Descriptive statistics for subjects with comorbidities
- Descriptive statistics by NYHA classification

Acceptable assay performance data are defined in respective assay design input document(s) (DIDs) and external assay performance requirements.

 BECKMAN COULTER	Access BNP Clinical Performance Evaluation Statistical Analysis Plan	Document #: NA
------------------------------------------------------------------------------------------------------	---------------------------------------------------------------------------------	--------------------------

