## Study Design and Sample Size

### Study Design

This is a prospective-multicenter controlled clinical study to evaluate diagnostic accuracy and ability to assess heart failure severity of the Access BNP assay. A one-time blood sample is collected from consented and enrolled subjects, within 4 hours of presentation, representing the intended use population (adult subjects presenting with clinical suspicion of new onset heart failure or worsening symptoms suggestive of decompensated or exacerbated heart failure).

Clinical performance of the Access BNP Assay will be evaluated as an aid in the diagnosis and assessment of severity in adults suspected of having new onset heart failure or decompensated or exacerbated heart failure. Diagnostic parameters (i.e., sensitivity and specificity) will be defined by subjects' HF status as indicated by the IUO assay relative to the subjects' final clinical HF status.

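### Does the plan need changing because it does not say whether the site heart failure diagnosis was masked to routine BNP or NT-proBNP?

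*SAP*

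**What the plan says.** The reference for both primary proportions is the enrolling site's diagnosis. SAP, Primary Endpoints, defines them as "sensitivity and specificity between Access BNP assay and final clinical HF status (determined by site diagnosis", and the two-by-two table under SAP, Statistical Methods uses the same reference.

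Protocol section 3.1 says of BNP and NT-proBNP that they "are standard-of-care biomarkers measured at patient presentation in the emergency department (ED) for patients presenting with signs and symptoms suggestive of heart failure". It describes raised concentrations as "permitting their use in supporting a clinical diagnosis of HF (but not used alone for this purpose". SAP, Study Design adds: "A one-time blood sample is collected from consented and enrolled subjects, within 4 hours of presentation". Protocol section 3.6 labels the marketed comparator, like the new assay, "as an aid in the diagnosis of congestive heart failure (also referred to as heart failure".

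On bias control, Protocol section 16 introduces its list with "The following requirements are strictly followed to prevent and minimize potential biases", and the SAP has a parallel list. Each has three items, on excluding results, retesting and discrepancy resolution. The nearest masking text, Protocol section 6.3, reads "Site personnel do not have access to medical standard of care test results". It concerns staff running the assay at the testing sites.

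The SAP introduction places conduct of the study under the enrolment protocol BNP-05-24. The subgroup lists in SAP, Additional Endpoints and Additional Analyses give age, sex and comorbidities as examples and are expressly open. On acceptance limits the SAP says: "Acceptable assay performance data are defined in respective assay design input document(s) (DIDs) and external assay performance requirements".

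**The concern.** A diagnostic accuracy estimate is only as independent as its reference. If a clinician who sees a low routine BNP tends to conclude that the patient does not have heart failure, some patients whom the new assay would have missed are reclassified as disease-free. They leave the false-negative cell, and sensitivity at a rule-out cutoff looks better than it is. The score interval cannot show this, because it reflects sampling error only.

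The documents make the situation plausible. The marker is routine in the emergency department, the study sample is taken close to presentation, and nothing in either text rules out that the result was seen. The SAP's bias section also calls the reference the true clinical status, which suggests the question was not considered. No listed analysis separates subjects diagnosed with a routine result in hand from those without. A sensitivity claim resting on 400 heart failure subjects could in principle be overstated with no trace in the tables.

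**Working it through.** **Inputs.** From SAP, Sample Size: sensitivity 82% against a lower bound of 75% with 400 HF positive subjects; specificity 98% against 95% with 600 HF negative; prevalence 40%. From SAP, Statistical Methods: two-sided 95% score interval. Two quantities are in neither document and are assumed: *q*, the share of site diagnoses that follow the routine marker, and *a*, the probability that the marker agrees with the new assay at the cutoff, taken as independent of true status.

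**The plan's own figures reproduce.** Sensitivity power by the normal approximation is Φ[(0.07 − 1.96·√(0.75·0.25/400)) / √(0.82·0.18/400)] = 92.4%. Exact power with the score limit (success at 317/400 or more) is 93.1%. Stated: above 92%. Specificity by the same formula is 98.6%. Stated: above 98%.

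**Expected cells per 1,000 subjects.** TP 328, FN 72, TN 588, FP 12. An observed 328/400 has a score lower limit of 77.9%.

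**Three ways a seen marker could act.**

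- Both directions: TP′ = (1−q)·TP + q·a·(TP+FP); FN′ = (1−q)·FN + q·(1−a)·(TN+FN).
- Removes diagnoses only: TP′ = TP·[1 − q(1−a)]; FN′ = FN·(1 − q·a).
- Adds diagnoses only: TP′ = TP + q·a·FP; FN′ = FN + q·(1−a)·TN.

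Apparent sensitivity TP′/(TP′+FN′) at q = 20%, true value 82%:

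| Agreement a | Both | Removes only | Adds only |
|---|---|---|---|
| 100% | 85.2% | 85.1% | 82.1% |
| 95% | 83.6% | 84.8% | 80.9% |
| 90% | 82.0% | 84.5% | 79.8% |
| 85% | 80.5% | 84.2% | 78.6% |

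For example, both directions at 95%: TP′ = 0.8·328 + 0.2·0.95·340 = 327.0; FN′ = 0.8·72 + 0.2·0.05·660 = 64.2; 327.0/391.2 = 83.6%.

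**Break-even agreement.** Above it sensitivity is overstated, below it understated.

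- Both directions: a/(1−a) = (0.82/0.18)·(0.66/0.34) = 8.84, so a = 89.8%. Over the SAP's 30% to 50% prevalences it runs from 92.8% to 86.3%.
- Removes only: TP shrinks by q(1−a) and FN by q·a, so a = 50%.
- Adds only: a/(1−a) = (0.82/0.18)·(588/12) = 223, so a = 99.6%.

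The threshold therefore depends on the assumed behaviour, on which the documents say nothing.

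**Share needed to bring the lower limit to 75%.** Correcting an observed 328/400 and 588/600 backwards:

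| Agreement a | Both | Removes only |
|---|---|---|
| 95% | q = 27.6% | q = 18.4% |
| 92% | not reached | q = 19.7% |
| 90% | not reached | q = 20.6% |
| 85% | not calculated | q = 23.4% |

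**No safe share either.** Fifteen extra false negatives give 328/415 = 79.0%, with a lower limit of 74.9%. That is 1.5% of 1,000 subjects. If a routine result were available in only 15% (150 subjects), 15 such cases among them would be enough. A small available share is reassuring only if following the marker is unrelated to disease and assay result.

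**What a breakdown by availability would yield.** Suppose 20% had no routine result, giving 80 HF positive subjects against 320. In the smaller group 82% has a score interval of 72.2% to 88.9%. A true gap of 2 to 4 points (84% or 86% against 82%) would be detected in about 7% or 15% of trials (4,000 simulated trials, Newcombe interval for the difference).

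**The case for a change.** The case for acting is that the SAP has a dedicated bias section, which is where a reader looks for a statement on masking, and that an open subgroup list is not pre-specification. A cross-reference to BNP-05-24 costs a line. If the diagnosis turns out to have been unmasked, the count of subjects with a routine result is cheap and informative. The effect need not be trivial: with true sensitivity at 75% and specificity at 98%, the chance that the lower limit clears 75% rises from 2.7% to 22% if 20% of diagnoses follow a marker agreeing 95% of the time in both directions.

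Part of this stands. The two documents are silent, and calling the reference the true status is loose wording; the SAP's own endpoint and methods sections name it correctly as the site diagnosis. The 22% is correct under its assumptions.

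The rest does not carry. The 22% depends on a chosen share, agreement level and direction, none of which has support in the documents. The 75% is a sample-size planning bound; the acceptance limits are in design input documents not available here. At the 90% sensitivity and 76% specificity cited in Protocol section 3.1, the two-way model does not bring the lower limit to 75% until q = 40%. Specificity there could look better than it is (76% appearing as 79.2% at q = 20%, a = 95%), but that rests on the same unknowns. The count measures availability rather than influence, and subjects without a routine result are a selected group, so their estimate cannot stand in for the whole.

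**Conclusion.** No change to the plan is called for. What has been found is a detail absent from these two documents on a matter that the SAP places under BNP-05-24. Nothing in the protocol or SAP is contradicted, and the sample-size figures reproduce.

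The possible bias is conditional on an unmasked diagnosis, and its size and sign cannot be fixed from the documents. At the planning values with q = 20%, and agreement between 85% and 100%, apparent sensitivity lies between 3.4 points below and 3.2 points above the true 82% across the three behaviours (82 − 78.6 and 85.2 − 82). No agreement threshold and no safe share with a routine result can be stated without choosing a model.

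A further informational table would not alter the primary estimates, could not separate bias from case mix, and would seldom detect a gap of the size in question. The open subgroup lists already allow it if the sponsor wants it. Should the enrolment protocol prove to have left the diagnosis unmasked, saying so beside the results is ordinary reporting practice and needs no amendment. The loose use of the word true in the SAP's bias section is clerical.

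This conclusion assumes that BNP-05-24 describes how the site diagnosis is reached, which could not be checked.
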